3.0 STATISTICAL HYPOTHESES AND DECISION RULES

3.1 Statistical Hypotheses

Not applicable

3.2 Statistical Decision Rules

Not applicable

3.3 Multiplicity Adjustment

Not applicable

4.0 SAMPLE-SIZE DETERMINATION

The planned sample size of 8 participants in each HI arm is not based on power calculations and is considered adequate to provide a descriptive characterization of the PK of soticlestat [REDACTED] [REDACTED] in participants with moderate or mild HI compared to healthy participants with normal hepatic function.

Any participant who is not PK evaluable including those experiencing emesis within 8 hours post dose may be replaced at the discretion of the Investigators in consultation with the sponsor to ensure 8 PK-evaluable participants in each arm of participants with HI and 12-24 PK-evaluable participants in matched participants with normal hepatic function complete.

5.0 ANALYSIS SETS

5.1 Safety Analysis Set

All participants who received the dose of soticlestat will be included in the safety evaluations.

5.2 Pharmacokinetic Analysis Set

All participants who comply sufficiently with the protocol and display an evaluable PK profile (eg, exposure to treatment, availability of measurements and absence of major protocol violations) will be included in the statistical analyses.

6.0 STATISTICAL ANALYSIS

6.1 General Considerations

All PK analyses will be conducted using Phoenix® WinNonlin® Version 8.1, or higher. All statistical analyses will be conducted using SAS® Version 9.4. All data recorded on the case report form (CRF) will be listed by hepatic function group and participant. All table, figure, and listing (TFL) shells and numbering list will be included and specified in the TFL Shells document.

The number of observations (n) will be presented as an integer (no decimal places), arithmetic mean (mean), median, and geometric mean (geom mean) values will be presented to 1 more level of precision than the individual values. Standard deviation (SD) and standard error of the mean (SEM) will be presented to 2 more levels of precision than the individual values. Minimum and maximum values will be presented to the same precision as the individual values. Arithmetic percent coefficient of variation (CV%) and geometric percent coefficient of variation (geom CV%) will be presented to 1 decimal place.

Geometric least-squares means (LSMs) will be reported with 1 more level of precision than the individual data. Geometric mean ratios (GMRs) and 90% confidence intervals (CIs) for the GMRs will be reported using 2 decimal places.

Noncompartmental analyses will be used in this study. Concentration values below the lower limit of quantitation (BLQ) will be presented as 'BLQ' in the concentration table listings and footnoted accordingly. BLQ values will be treated as zero for the calculation of summary statistics, the generation of concentration plots, and the calculation of PK parameters, unless they are deemed questionable (e.g., BLQ value between measurable values), in which case they will be treated as missing and excluded from the concentration summary statistics and the PK analysis. Values of 0 are not included in the calculation of geom mean and geom CV%.

A participant's PK parameter data will be included in the listings but may be excluded from the descriptive and inferential (linear mixed-effects model) statistics if one or more of the following criteria are met:

- A predose (0 hour) concentration is greater than 5% of that participant's maximum concentration value for the given hepatic function group
- A participant did not meet inclusion/exclusion criteria that may have an effect on the PK (as determined by the Takeda Pharmacology Lead and Celerion Pharmacokinetic Scientist)
- A participant deviates substantially from the protocol defined study procedures including but not limited to dosing, dose timing, sample collection, meal timing, etc. (as determined by the Takeda Clinical Pharmacology Lead and Celerion Pharmacokinetic Scientist)
- A participant may be excluded due to vomiting

The details on PK parameter calculations and TFLs will be outlined in the clinical pharmacology and analysis plan (CPAP) and TFL Shells document including specifics on the following:

- For participants with $AUC_{\text{extrap}}\%$ greater than 20%, the descriptive and model-based statistics for AUC_{∞} will be presented with and without these participants included, if appropriate
- PK parameters presented by hepatic function group, including the units, precision, and summary statistics that will be presented in in-text and end-of-text tables
- Concentration data presented by hepatic function group, including the units, precision, and summary statistics that will be presented in end-of-text tables
- Concentration data file used for PK analysis
- PK parameter Phoenix[®] WinNonlin[®] output file used to generate the TFLs
- ANOVA model results presented in in-text and end-of-text tables
- Arithmetic mean concentration-time figures presented as in-text and end-of-text figures

- Individual concentration-time figures presented in Appendix 16.2.6.

Fraction unbound will be calculated based on the ratios of unbound concentration relative to total concentration at 0.5 and 10 hours postdose for each subject as follows:

$F_u = C_{u,0.5\text{ hrs}}/C_{0.5\text{ hrs}}$ and $F_u = C_{u,10\text{ hrs}}/C_{10\text{ hrs}}$ (where $C_u =$ unbound concentration in plasma at time t and $C_t =$ total concentration in plasma at time t).

Continuous demographic and safety data will be summarized descriptively. For categorical variables, the count and percentages of each possible value will be tabulated, where applicable. The denominator for the percent calculation will be the number of participants in the safety set for overall summaries, and the number of participants dosed in each hepatic function group in hepatic function group summaries. For continuous variables, n, mean, SD, minimum, median, and maximum values will be tabulated. The level of precision will be presented as follows: minimum/maximum in the same precision as in the database, mean/median in one more precision level than minimum/maximum, SD in one more precision level than mean/median, and n will be presented as an integer. Counts and percentages will be presented to 1 decimal place. Baseline is defined as the last observation prior to dosing.

If additional normal hepatic function participants are added to match the mild HI group due to differences in matching criteria, then disposition and demographic summaries for the normal hepatic function group may be separated based on matching to moderate HI or mild HI.

6.1.1 Handling of Treatment Misallocations

Not applicable

6.2 Study Information

A study information table will be generated including the following items: date of first participant's signed informed consent form, date of dosing, date of last participant's last visit/contact, date of last participant's last procedure for collection of data for primary endpoint, the version of Medical Dictionary for Regulatory Activities (MedDRA®), the version of World Health Organization (WHO) Drug Dictionary, and SAS version used for creating the datasets.

6.3 Disposition of Participants

Disposition of participants (number of participants dosed, completed the study, discontinued from the study, discontinued from the study drug, and reason(s) for discontinuation(s)) will be summarized by matched hepatic function group (ie, Severe HI, Moderate HI, Mild HI, Normal Hepatic Function (Mild), Normal Hepatic Function (Moderate), Normal Hepatic Function (Overall)) and overall. Study completion status, including reason for discontinuation, will also be listed by hepatic function group and participant.

6.4 Demographic and Other Baseline Characteristics

6.4.1 Demographics

Demographic and baseline characteristics will be summarized descriptively matched hepatic function group (ie, Severe HI, Moderate HI, Mild HI, Normal Hepatic Function (Mild), Normal Hepatic Function (Moderate), Normal Hepatic Function (Overall)) and overall. Summary statistics (n, mean, SD, minimum, median, and maximum) will be generated for continuous variables (age as collected on CRF, weight, height, and BMI) and the number and percentage of participants within each category will be presented for categorical variables (sex, race, and ethnicity). The last height, weight, and BMI recorded prior to dosing will be used in the baseline summaries. Demographics data will also be listed as recorded in the case report form (CRF), including the date of informed consent.

6.4.2 Medical History and Concurrent Medical Conditions

Medical history will include determining whether the participant has any significant conditions or diseases that resolved at or before signing the informed consent form (ICF). Concurrent medical conditions are those significant ongoing conditions or diseases that are present at signing the ICF. Each participant's medical history and concurrent medical conditions will be listed. Any medical condition started after taking the study drug will be classified as an adverse event. All medical history will be coded using the MedDRA® Version 24.1. The medical history listing will include the system or organ class (SOC) involved, preferred term (PT), start date (if known) and end date (if known) or whether the condition was ongoing, and a description of the condition or event. There will be no analysis of medical history.

6.4.3 Baseline Characteristics

Child-Pugh scores will be assessed at screening to classify participants into hepatic function groups. Two hepatic function assessments are required prior to Day 1 for participants with HI. These 2 assessments should be obtained during screening and at least 48 hours apart. In the case where a participant has an available historical Child-Pugh assessment score within 3 months prior to screening, 1 assessment can be conducted during the screening period. If the results of the 2 assessments indicate different liver function categories, a third assessment must be conducted at least 24 hours after the second assessment. The last recorded scores will be summarized (n, mean, SD, minimum, median, and maximum) by hepatic function group and presented in the demographic summary table. Individual results will be listed by hepatic function group and participant.

6.5 Medication History and Concomitant Medications

Medication history will include any medication relevant to eligibility criteria and safety evaluation stopped at or within 28 days prior to signing the ICF. Concomitant medication includes any medication other than study drug taken at any time between ICF and the end of the study (including follow-up visit). All medication history and concomitant medications recorded

during the study will be coded with the WHO Global Dictionary September 2021 and listed. If appropriate, the listing will include the medication name, coded term, dosage, route of administration, start date and end date, or whether it continued after study completion, and indication for use. There will be no statistical analysis of medication history or concomitant medications.

6.6 Efficacy Analysis

Not applicable

6.7 Safety Analysis

Safety will be evaluated by the incidence of TEAEs, severity and relationship of TEAEs, and changes from baseline in the participants' clinical laboratory results, vital signs, and 12-lead ECGs using the safety set. Clinically significant laboratory values, vital signs, ECGs, and CSSRS results will be reported as AEs. All safety data will be listed by hepatic function group (ie, Severe HI, Moderate HI, Mild HI, Normal Hepatic Function), participant, and assessment time points, including rechecks, unscheduled assessments, and early termination (ET) assessments, chronologically.

Continuous variables will be summarized using n, mean, SD, minimum, median, and maximum. Frequency counts and percentages will be reported for categorical data when appropriate. Where individual data points are missing because of dropouts or other reasons, the data will be summarized based on reduced denominators. If additional normal hepatic function participants are added to match the mild HI group, then the normal hepatic function group will be separated based on matching to moderate HI or mild HI.

6.7.1 Adverse Events

All AEs captured in the database will be listed in by-participant data listings including verbatim term, coded term, severity (mild, moderate, severe), relationship to study drug (related or not related), frequency, and action relative to the study drug as recorded in the CRF. All AEs occurring during this study will be coded using the MedDRA® Version 24.1. Only TEAEs will be summarized.

A TEAE is defined as an AE that is starting or worsening at the time of or after dosing of study drug.

If the onset time of an AE is missing and the onset date is the same as the dosing date, then the AE will be counted as treatment-emergent. If the onset date of an AE is missing, then the AE will be considered treatment-emergent, unless the AE is known to have started prior to dosing. If severity is missing, the AE will be counted as severe, and if relationship is missing, the AE will be counted as related.

TEAEs will be tabulated by hepatic function group (ie, Severe HI, Moderate HI, Mild HI, Normal Hepatic Function), SOC, and PT. Summary tables will include the number and percent of participants reporting the TEAE by hepatic function group. In addition, the number and

CONFIDENTIAL

percent of TEAEs for each hepatic function group will be summarized. Tables for the most commonly reported non-serious TEAEs (ie, those events reported by >1 participant in one or more hepatic function groups, and TEAEs that are >5% of total TEAEs (or >1 event if fewer than 20 TEAEs), excluding serious adverse events (SAEs)) and for SAEs only, will also be presented. The denominators for percent calculations will be the number of participants dosed or number of events for each hepatic function group.

Additional TEAE summary tables for participants and events will be presented by severity and relationship to study drug. If a participant experiences the same TEAE at more than one level of severity, the participant will be counted in the most severe category only. For relationship to study drug, if a participant has both related and unrelated TEAEs with the same term, the participant will be counted in the related category.

An overview summary table of TEAEs, including the number of participants with TEAEs, SAEs, treatment-related TEAEs, treatment-related SAEs, TEAEs by severity, and AEs leading to study discontinuation will be provided.

Should any SAEs (including all-cause mortalities) occur, they will be summarized in the same way as TEAEs. All AEs will be displayed in the data listings and TEAEs will be discussed in the text of the clinical study report (CSR).

6.7.2 Adverse Events of Special Interest (if applicable)

Not applicable

6.7.3 Clinical Laboratory Assessments

Hematology, serum chemistry, coagulation, and urinalysis will be performed at screening, Day -1, Day 3, and Day 7 (or at ET if applicable). Urine drug screening will be carried out at screening and Day-1 only. For female participants, a pregnancy test will be performed at screening and check-in and FSH will be checked at screening. In addition, laboratory safety tests may be performed at various unscheduled time points, if deemed necessary by the Investigator.

For all laboratory values that are numeric, summary statistics (n, mean, SD, minimum, median, and maximum) will be presented for each laboratory test by hepatic function group (ie, Severe HI, Moderate HI, Mild HI, Normal Hepatic Function) and time point of collection. Change from baseline will be summarized in a similar manner. Baseline is defined as the last assessment, including recheck and unscheduled assessments, taken prior to dosing. All clinical laboratory listings and tables will be presented in international system (SI) units. Postdose unscheduled or recheck assessments will not be used in analysis. Similarly, ET results will not be included in summaries.

For calculation of summary statistics, lab results below or equal to lower limit of quantification (LLOQ) will be set to LLOQ/2 if a LLOQ value has been defined, and otherwise will be set to missing; lab results above or equal to upper limit of quantification (ULOQ) will be set to ULOQ

if a ULOQ value has been defined, and otherwise will be set to missing. Listings will display the original result received from the laboratory.

Out-of-normal range flags will be recorded as follows: high (H) and low (L) for numerical results and did-not-match (*) for categorical results. For each laboratory test, a shift table will be developed comparing the frequency and percentage of the results at baseline (above normal (H), normal (N), or below normal (L)) with the postdose time points. For urinalysis tests, the categories are normal (N) and abnormal (A). Out-of-range values and corresponding recheck results will be listed.

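### The SAP's laboratory limit rule halves results equal to the LLOQ and, read literally, drops `<x` or `>x` results when no limit is defined; a small wording fix to descriptive safety summaries

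*SAP*

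**What the plan says.** SAP 6.7.3 gives one rule for laboratory results at or beyond a quantification limit.

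- Lower side: "lab results below or equal to lower limit of quantification (LLOQ) will be set to LLOQ/2 if a LLOQ value has been defined". If no LLOQ is defined, the result becomes missing.
- Upper side: "lab results above or equal to upper limit of quantification (ULOQ) will be set to ULOQ", on the condition "if a ULOQ value has been defined, and otherwise will be set to missing".
- Scope: the rule opens with "For calculation of summary statistics, lab results below or equal to lower limit of quantification (LLOQ", so it governs summary statistics only.
- Statistics affected: "summary statistics (n, mean, SD, minimum, median, and maximum) will be presented for each laboratory test by hepatic function group" and time point. In addition, "Change from baseline will be summarized in a similar manner".
- Retained elsewhere: "Listings will display the original result received from the laboratory". The same section plans high/normal/low shift tables and a listing of out-of-range values with their rechecks. The limit rule names neither.

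SAP 6.7 bases the safety evaluation partly on "changes from baseline in the participants' clinical laboratory results, vital signs, and 12-lead ECGs using the safety set", and says that clinically significant laboratory values are reported as AEs.

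Two other places bear on the rule. For PK concentrations, SAP 6.1 treats only values below the lower limit as BLQ; equality is not included. SAP 9.2, Data Handling Conventions, is marked not applicable, so no other section says when a laboratory limit counts as defined.

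**The concern.** There are two separate defects.

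**Equality at the lower limit.** The LLOQ is the lowest value that the assay can quantify, so a result equal to it is a measurement. Imputing half the limit is a convention for results known only to lie below it. Applied to equality, it replaces a known value with one that is too small. This differs from the SAP's own PK convention. It also differs from the upper side, where a result equal to a defined ULOQ keeps its value.

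**Missing when no limit is defined.** If no limit is on file, a result can be recognised as beyond a limit only from the form in which it was reported, `<x` or `>x`. That form already supplies the bound x. Setting the result to missing discards the bound. For `>x`, it removes a value known to be high from n, mean, SD, median, maximum and change from baseline.

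At stake are the numeric laboratory summaries by hepatic function group. Each HI arm has 8 participants, so a single result can move a group mean or set the maximum.

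**Working it through.** The plan states no figure for this rule, so there is nothing to reproduce. The checks below are direct arithmetic on its wording.

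**Inputs.** From the documents: 8 participants per HI arm and 12 to 24 with normal hepatic function (SAP 4.0). Not in the documents, and therefore assumed: the laboratory limits, the number of results at or beyond them, and the level of the other results.

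**1. Change from baseline, in LLOQ units (L).** The SAP rule is compared with halving only results strictly below L.

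| True values | Strictly-below rule | SAP rule |
|---|---|---|
| 1L, then 2L | 2 − 1 = +1.0L | 2 − 0.5 = +1.5L |
| 2L, then 1L | 1 − 2 = −1.0L | 0.5 − 2 = −1.5L |
| below L, then 1L | 1 − 0.5 = +0.5L | 0.5 − 0.5 = 0 |

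A change between 1L and 2L is overstated by 50%. A rise from below the limit to exactly the limit disappears.

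**2. Arm mean with k of n results tied at the LLOQ.** Each tie loses L/2, so the shift is −kL/(2n).

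| n | k = 1 | k = 3 |
|---|---|---|
| 8 | −0.0625L (L/16) | −0.1875L |
| 12 | −0.0417L | −0.125L |
| 24 | −0.0208L | −0.0625L |

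**3. One result reported as `>U`, no ULOQ defined.** Let the other n − 1 results average mU. The literal rule gives a mean of mU. Using the reported bound gives ((n − 1)m + 1)U/n. The understatement is 1 − m/[((n − 1)m + 1)/n].

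For n = 8 and m = 0.1, the mean using the bound is (0.7 + 1)/8 = 0.2125U and the understatement is 1 − 0.1/0.2125 = 52.9%. For n = 8 and m = 0.8, it is (5.6 + 1)/8 = 0.825U and 1 − 0.8/0.825 = 3.0%.

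| n | m = 0.1 | m = 0.3 | m = 0.5 | m = 0.8 |
|---|---|---|---|---|
| 8 | 52.9% | 22.6% | 11.1% | 3.0% |
| 12 | 42.9% | 16.3% | 7.7% | 2.0% |
| 24 | 27.3% | 8.9% | 4.0% | 1.0% |

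The maximum becomes the largest remaining result instead of at least U. The change from baseline for that visit cannot be computed.

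**4. How close to the limit must an analyte lie?** Illustration by simulation: lognormal results, CV 40% or 60%, reported in steps equal to the LLOQ, 400,000 values per scenario. The SAP's equality rule is compared with halving only results strictly below the limit.

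| Arm median | Change in mean |
|---|---|
| 1 LLOQ | −27% to −36% |
| 1.5 LLOQ | −13% to −15% |
| 2 LLOQ | −5% to −6% |
| 4 LLOQ | −0.1% to −0.4% |

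The equality defect therefore matters only for an analyte whose typical values sit within about twice its LLOQ.

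**The case against.** The strongest reply is that the rule may never act. The documents give no limit for any laboratory test and do not show that any analyte in the panel (Protocol 9.2.9.1) runs near one. As step 4 shows, the effect on the mean is at most 0.4% once the median is four times the LLOQ. The summaries are descriptive, and the SAP specifies no hypotheses. All of this stands and limits the weight of the point.

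A second reply concerns intent. The equality clause may be meant for below-limit results that the laboratory stores as the limit value, and a result reported as `>x` may be taken to define its own limit. Either reading would be sensible, but the SAP states neither. The reply therefore supports a clarification; it does not remove the need for one.

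Three stronger readings are tempting, and the documents do not support them.

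- *The laboratory tables are wrong.* They are affected only if a result ties with an LLOQ or lies beyond a limit not held in the data. Nothing shows that either occurs.
- *The rule conceals the worst values.* It covers summary statistics only. Listings keep the original result, out-of-range values are listed, shift tables are produced, and clinically significant values are reported as AEs. These displays do not fully replace the numeric summaries: a participant already high at baseline who rises further stays high-to-high in the shift table, and postdose rechecks are not used in analysis. The values nevertheless remain visible in the report.
- *With no LLOQ defined, all results at or below the limit vanish and the mean rises sharply.* Without a defined limit, a numeric result cannot be identified as equal to it and stays in the summary. Only results reported as `<x` could become missing. In the scenarios of step 4 with medians of 1 to 2 LLOQ, the mean then rises by about 0.01% to 7%, and by at most 1.7% at medians of 1.5 LLOQ or more.

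Nor do the documents support naming a test or an arm in which ties would concentrate.

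**Conclusion.** The point holds as a minor defect of wording. As written, the rule assigns half the true value to a result equal to the LLOQ, against the SAP's own PK convention. Read literally, it also discards a usable bound when no limit is defined.

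The size in this trial is unknown and may be zero for many tests. The conditional figures are LLOQ/16 off the mean per tied result in an arm of 8, and a 3% to 53% understatement of the mean for one dropped `>U` result in 8. The second range assumes that the other seven average 0.8U to 0.1U. The consequences are confined to descriptive laboratory summaries; the primary PK analysis is unaffected. It is worth correcting because the correction is cheap, but it does not threaten any conclusion of the study.

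**What to change.** Reword the rule in SAP 6.7.3 as follows:

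- Set a result to LLOQ/2 only if it is strictly below the LLOQ, and use a result equal to the LLOQ as reported.
- Set results above the ULOQ to the ULOQ.
- If a result is reported as `<x` or `>x` and no limit is on file, take x as the limit instead of setting the result to missing.
- Footnote each affected table with the number of imputed results.

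If the equality clause was meant for below-limit results stored as the limit value, say so and identify them by the reported `<` sign.

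The cost is about two sentences in the SAP and a small change to the laboratory dataset program. No new data are needed.
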